11.6 Alternative Treatments

There are no alternative treatments. Patients who are participating in another interventional study will be ineligible for this study. Participants will be told they have the option to choose not to participate in this study. The primary team will manage the participants' clinical condition according to their best clinical judgment. Any potential treatments for acute hypoxic respiratory illness, including low tidal volume ventilation in patients requiring mechanical ventilation will be allowable, determined by the primary medical team, and not restricted by participating in this study. The blinded study drug material will be added to the treatment course that the primary team considers appropriate.

11.7 Potential Benefits

The potential benefits to science and mankind that may result from this study include the knowledge that we will obtain regarding the effects of citrulline and the urea/NO cycle on inflammation and oxidative stress in an acute hypoxic respiratory illness. In addition, we will also gain valuable information regarding the safety of IV citrulline in COVID-19 (SARS-CoV2) infected patients. Since the urea/NO cycle and NOS play an integral role in redox homeostasis, administration of citrulline may decrease oxidative stress and improve organ function, especially pulmonary function, even potentially mitigating acute lung injury in these patients. The patients randomized to the placebo arm will not directly benefit from participating in this study but will provide vital information for the interpretation of the study results and a valuable contribution to medical science.

These benefits are reasonable in relation to the relatively few known risks of L-citrulline. L-citrulline, by re-establishing urea/NO cycle homeostasis and reducing oxidant stress, may improve clinical outcomes, including mitigation of organ dysfunction, particularly lung injury. These improved outcomes are desirable by all patients seeking medical attention. L-citrulline has been used in humans previously and has been shown to be safe.

12.0 DATA HANDLING AND RECORDKEEPING

12.1 Sources of Research Material

All materials will be collected and recorded for research purposes. The data collected during this investigation will be obtained from multiple sources, including medical records, observational data, and serum samples. One of the main sources of data will be chart abstraction utilizing the patient's medical record. The progress notes and bedside nursing notes and daily charting will also be used to collect data. Interviews with patients and/or patients' family will be conducted both in person and over the phone on occasion. The patients will have serum samples collected at the specified timepoints for specialized laboratory analyses. All the remaining data will be derived from the interactions with the patient in the form of the nurses' and physicians' examinations and interviews.

12.2 Participant Confidentiality

The investigators affirm and uphold the principle of the participant's right to protection against invasion of privacy. Throughout this study, a participant's source data will only be linked to the clinical study database or documentation via a unique study identification number. As permitted per HIPAA regulations, limited participant attributes such as sex, age, or gender may be used to verify the accuracy of the participant's unique identification number. Copies of any participant source documents provided to entities outside of the University of Arkansas for Medical Sciences (including the FDA, IRB, or NIH) will have all personally identifiable information removed (e.g., participant name, address, date of birth)

The research coordinator, principal investigator, or co-investigators will collect data and record it on case report forms designed specifically for the study. The data will then be entered in a password protected, privacy-secured, computer database. The data collection forms will be kept in a locked cabinet in a locked office at each site. Only the study investigators and study coordinators will have access to the locked cabinet. All samples obtained for this study will be assigned a code which will not identify the subject. The only key to the code will be in the password-protected computer database. The Principal Investigator will be responsible for maintaining confidentiality of data and codes. Only study investigators and the study coordinator will have access to the code and information that identifies a volunteer as a being in this study. The results of analyses run on those samples will not be reported to the participant or primary team. The codes linking the patients with their data will be destroyed after all participants have completed the study and the data has been through quality assurance processes.

12.3 Case Report Forms

CRFs will be completed for each participant randomly assigned to study medication or placebo. CRFs will be completed in legible black ink and will be written in English. Corrections will be made via a single line strikeout of the incorrect information and writing in the revisions. All corrections must be initialed and dated. The completed original CRFs are the sole property of site where enrolled.

12.4 Medrio Computerized Database

Medrio EDC will be used as the data capture tool. It is a secure, cloud-based application that provides 1) intuitive navigation for validated data entry; 2) detailed audit trails for tracking data manipulation (e.g. old/new/deletion, approvals, locking); 3) reporting modules and on-demand data extraction capabilities; and 4) tools for importing data from external sources.

Data within Medrio is siloed and independently structured to ensure that a study and its users can access only their own study. Thus, only study personnel for this project with appropriate permissions will be allowed to access the database. Authorized users can input data into Medrio from anywhere in the world with secure web authentication and data logging.

12.5 Record Retention

The investigator will keep all study-specific documents, an identification log of all participating patients, source worksheets, original signed and dated informed consent documents in a locked and secure office or storage space until at least three years after the completion of the study. In addition, the secure Medrio database will be maintained for at least three years after completion of the study. The data will be housed with the sponsor from the Medrio EDC.

APPENDIX A: Schedule of Events

Measurement	Day 0 (baseline)	Day 1	Day 2	Day 3	Day 4	Day 5	Day 6	Day 7	Day 8	Day 9	Day 10	Day 11	Day 12-DC	Day 28 ^e Follow-up	Day 60 ^e Follow-up
Informed Consent	X														
Demographics- Hx & Px	X														
Eligibility Assessment	X														
Pregnancy Test	Xc														
Study Drug Administration		X	X	X	X	X	X	X	X	X					
Vital Signs		X	X	X	X	X	X	X	X	X	X	X	X		
Mean Arterial Pressure		Xa,b,d	X	X	X	X	X	X	X	X	X	X			
Vasopressor Dosages		Xa,b,d	X	X	X	X	X	X	X	X	X	X			
Basic Metabolic Panel		A	A	A	A	A	A	A	A	A	A	A			
CBC		A	A	A	A	A	A	A	A	A	A	A			
LFTs		Ab	A	A	A	A	A	A	A	A	A	A			
D-dimer blood draw		Xa,b	X		X		X		X		X		X		
CRP		Xa,b	X		X		X		X		X		X		
5 ml blood for citrulline etc.		Xa,b	X		X		X		X		X				
SaO2/ FiO2 ratio		X	X	X	X	X	X	X	X	X	X	X			
PaO2		X	X	X	X	X	X	X	X	X	X	X			
ABG		A	A	A	A	A	A	A	A	A	A	A			
Hospital status		X	X	X	X	X	X	X	X	X	X	X	X	X	X
ICU status		X	X	X	X	X	X	X	X	X	X	X	X	X	X
Non-invasive ventilation status		X	X	X	X	X	X	X	X	X	X	X			
Invasive ventilation status		X	X	X	X	X	X	X	X	X	X	X			
ConMed Review		X	X	X	X	X	X	X	X	X	X	X	X	X	X

Adverse Event Review		X	X	X	X	X	X	X	X	X	X	X	X	X	X	X
----------------------	--	---	---	---	---	---	---	---	---	---	---	---	---	---	---	---

a= measurement should be recorded or performed at hours 0, 2 and 12

b= Day 1 hour 0 samples/procedure must be collected/recorded before study drug is administered.

c= only perform if patient is of childbearing potential

d= must be collected 15 minutes prior to administration of study medication

e= Day 28 and Day 60 are telephone follow ups

X= Study Procedure A= Standard of Care

APPENDIX B- Protocol Clarification Memo

MEMO TO FILE

DATE: 20 January 2021

STUDY NUMBER: CIT-COVID19-002-01

STUDY TITLE: Prospective, Randomized, Double-Blind, Placebo-Controlled Phase II Trial of Intravenous L-Citrulline to Delay and Potentially Prevent the Need for Invasive Mechanical Ventilation for Acute Hypoxic Respiratory Failure in Patients with COVID-19 (SARS-CoV-2) Illness

Protocol Version/Date: Version 2.0, 08 September 2020

[figure not shown]
RE: Protocol Clarification Memo: Requirements of Arterial Blood Gas (ABG) Timepoint

The diagnostic criteria for acute lung injury (ALI) and ARDS utilize the $\text{PaO}_2/\text{fraction of inspired oxygen (FiO}_2)$ [P/F] ratio measured by arterial blood gas analysis to assess the degree of hypoxemia. We hypothesized that the pulse oximetric saturation (SpO_2)/ FiO_2 (S/F) ratio can be substituted for the P/F ratio in assessing the oxygenation criterion of ALI/ARDS associated with SARS Cov2.

S/F ratios correlate with P/F ratios. S/F ratios of 235 and 315 correlate with P/F ratios of 200 and 300, respectively, for diagnosing and following up patients with ALI and ARDS.

UAMS Standard Of Care (SOC) protocol restricts arterial sample collection for ABGs and hence the need to issue the memo.

The ABG requirement in the protocol is not required but if the data is collected it will be entered into the Clinical Data Base.

DocuSigned by:

12/1/2020
Signer Name: [name]
Signing Reason: I approve this document
Signing Time: 20-Jan-2021 12:29:19 PM PST
[name], MPPM (Hon)
82500763261A481A9B13C5C30307C2EB1
Chief Medical Officer
Asklepion Pharmaceuticals, LLC

20-Jan-2021
Date

Protocol Clarification Memo Version 1.0 dated 20Jan2021 Final

APPENDIX C: Protocol Clarification Memo- Procedure Window Allowance

MEMO TO FILE

DATE: 03 March 2021

Protocol Number: CIT-COVID19-002-01

Protocol Title: Prospective, Randomized, Double-Blind, Placebo-Controlled Phase II Trial of Intravenous L-Citrulline to Delay and Potentially Prevent the Need for Invasive Mechanical Ventilation for Acute Hypoxic Respiratory Failure in Patients with COVID-19 (SARS-CoV-2) Illness

Protocol Version/Date: Version 2.0, 08 September 2020

RE: Protocol Clarification Memo- Procedure Window Allowance

During the trial's conduct, the procedures outlined below warrant an allowable window around the scheduled timepoint. These windows also allow for real world experience in the clinical trial.

1.0 PK/PD Blood Sample Collection:

Timepoint:	Procedure Window:
Hour 0	No Window
Hour 2	\pm 30 Minutes
Hour 12	\pm 30 Minutes
Day 2	\pm 30 Minutes within 24 hours from Hour 0 timepoint
Day 4	\pm 2 Hours
Day 6	\pm 2 Hours
Day 8	\pm 2 Hours
Day 10	\pm 2 Hours

2.0 PK/PD Blood Volume Clarification:

The minimum blood volume needed for the PK/PD analysis requires a minimum of 5 mL of whole blood. Given the tube sizes available, it is not possible to draw 5 mL of blood given that the required tube comes in 3 mL or 7 mL volume. If a sample should have more than 5 mL of blood drawn, it will not be considered a deviation. However, any blood volume under 5 mL will be recorded as a deviation as it may not provide enough plasma to run the assay. All samples will be processed even if the volume is not 1 mL plasma.

3.0 CRP and D-dimer Blood collection:

Memo to File (Protocol Clarification) Version 1.0 Dated 03 March 2021- Final

1

CRP and D-dimer blood collections will have an allowable procedure window of \pm 30-minutes from the scheduled blood collection time. Please see the table below. There will not be a procedure window for hour 0 blood collection.

Timepoint:	Procedure Window:
Hour 0	No window
Hour 2	\pm 30 Minutes
Hour 12	\pm 30 Minutes
Day 2	\pm 30 Minutes within 24 hours from Hour 0 timepoint
Day 4	\pm 30 Minutes
Day 6	\pm 30 Minutes
Day 8	\pm 30 Minutes
Day 10	\pm 30 Minutes

4.0 Follow-up Visit Day 28 and Day 60:

Timepoint:	Procedure Window:
Day 28 Follow-up	\pm 2 Days
Day 60 Follow-up	\pm 2 Days

The above procedure windows are allowed as this will allow for real-world evidence and not impact the analysis.

DocuSigned by:

 Signer Name: [name]
 Signing Reason: I approve this document
 Signing Time: 03-Mar-2021 | 9:07:03 AM PST
 8750D76626FA481AAFB13CB0307C2ED1

03-Mar-2021

[name], MFFPM (Hon)
 Chief Medical Officer
 Asklepion Pharmaceuticals, LLC

Date

Memo to File (Protocol Clarification) Version 1.0 Dated 03 March 2021- Final

2

15. Summary of Changes:

SECTION	DESCRIPTION of CHANGES
1.0	Protocol Version Date
2.0 STUDY SUMMARY	Study Design-D28 and D60 telephone follow up
2.0 STUDY SUMMARY	Treatment Arms-added independent pharmacist
2.0 STUDY SUMMARY	Sample Size/Statistical Considerations-added PaO2
2.0 STUDY SUMMARY	Primary Biochemical Efficacy Variables-added surrogate marker info
2.0 STUDY SUMMARY	Secondary Biochemical Efficacy Variables-added dose proportionality info
4.1 Primary Endpoints (objectives)	Primary Endpoints Objectives-added association of plasma amino acids
5.1 Study Description	Study Description-added telephone follow up for D28 and D60
6.4 Informed Consent	Informed Consent-added PK Sample explanatory analysis
7.1.5 Clinical Laboratory Tests	Clinical Laboratory Tests-added timepoints
7.2.2 On Study (days 0-DC) Assessments	On Study Assessments-added timepoints
10.2 General Statistical Approach	Clinical Outcomes-added D28 and D60
9.3 Pre-Existing Conditions	Pre-Existing Conditions-added SaO2/FiO2
10.2 General Statistical Approach	General Statistical Approach-added multiplicity adjustment approach
10.4 Sample Size	Data and Safety Monitoring Plan-added independent PK evaluation info
APPENDIX A: Schedule of Events	Schedule of Events-added footnotes to D28 and D60
APPENDIX A: Schedule of Events	Schedule of Events-added PaO2
APPENDIX A: Schedule of Events	Schedule of Events-added D-dimer test and CRP
APPENDIX A: Schedule of Events	Schedule of Events-added Conmed and AE review

Changes from Protocol Version 2.0 dated 08 September 2021 to Version 3.0 Dated 11 June 2021

Section	Description of Changes
1.0	Protocol Version and date were updated to reflect Version 3.0 dated 11 June 2021 and added the IND number.
Table of Contents	The table of contents was updated to reflect the addition of Appendix B and C.
2.0 Study Summary	Updated Section “Sample Size/Statistical Considerations:” to reflect that up to 66 participants can be enrolled.
5.1 Study Description	The wording is updated to reflect. Up to 66 participants can be enrolled.
6.1 Participant Enrollment	The wording is updated to reflect up to 66 participants can be enrolled.
10.4 Sample Size	The wording is updated to reflect up to 66 participants can be enrolled. The wording was also updated to account for the additional patients in the analysis
14.0 Investigator Signature Page	Updated the protocol version and date.
APPENDIX	Protocol Clarification Memo: Requirement of Arterial Blood Gas (ABG) Timepoint was added (APPENDIX B), and the Protocol Clarification Memo-Procedure Window Allowance was added (APPENDIX C)

## INTRODUCTION

This document outlines the planned statistical analyses for data collected within the scope of Asklepion L-Citrulline protocol CIT-COVID19-002-01, entitled “Prospective, Randomized, Double-Blind, Placebo-Controlled Phase II Trial of Intravenous L-Citrulline to Delay and Potentially Prevent the Need for Invasive Mechanical Ventilation for Acute Hypoxemic Respiratory Failure in Patients with COVID-19 (SARS-CoV-2) Illness”. This statistical analysis plan (SAP) applies to the protocol v3.0, 11 June 2021. The purpose of this plan is to provide general, and in some instances, specific guidelines for which the various analyses will proceed. The primary analysis will include clinical efficacy, biochemical efficacy, and safety data up to the primary analysis data cut-off date.

## OBJECTIVES

### Primary Endpoints (objectives)

The primary objectives of the study are as follows:

- The primary clinical objective is to evaluate the difference in the length of time to an intubation event in hours from the start of study infusion between the study arms.

### Secondary Endpoints (objectives)

The secondary objectives of this study are as follows:

- To evaluate the effects of intravenous L-Citrulline on plasma levels of citrulline and arginine in patients admitted to the hospital with COVID-19 infection (SARS-CoV2) and acute hypoxemic respiratory symptoms requiring oxygen therapy.
- To evaluate beneficial effect of intravenous L-Citrulline on hemodynamics.
- To evaluate the safety of intravenous L-Citrulline compared to placebo as measured by incidence of reported adverse events.
- To evaluate the effect of intravenous L-Citrulline compared to placebo as measured by the total length of all mechanical ventilation, including non-invasive modalities such as high flow nasal cannula and BiPAP and oxygen therapy.

- To evaluate the effect of intravenous L-Citrulline compared to placebo on Hospital all-cause mortality
- To evaluate the effect of intravenous L-Citrulline compared to placebo on lengths of ICU and hospital stay
- To evaluate overall difference in intubation rates
- To evaluate overall duration of mechanical ventilation from consent and post-infusion

## **STUDY DESIGN**

This is a randomized, double-blind, placebo-controlled, phase II study to evaluate the safety and efficacy of intravenous L-Citrulline in reducing the length of time from the start of study infusion to an intubation event in hospitalized acutely ill patients with an acute hypoxic respiratory illness due to COVID-19 infection (SARS-CoV2). Patients age of 18 years old and less than 65 years old inclusive with COVID-19 infection (SARS-CoV2) will be included in the study.

Only subjects hospitalized at UAMS and requiring oxygen for an acute hypoxic respiratory illness due to COVID-19 (SARS-CoV2) will be included in this study. Study drug administration will occur exclusively in the hospital.

In addition, subjects will receive standard supportive care for acute hypoxic respiratory illness and failure.

Approximately 60 participants ages 18 years to 65 years, inclusive, who meet all the inclusion criteria and none of the exclusion criteria will be randomized into the study over approximately 6-9 months.

The study consists of an initial Study Drug bolus followed by a continuous infusion for a maximum of 10 days. The safety and efficacy will be evaluated through hemodynamic monitoring, laboratory assessment, oxygenation status, and biomarker measurements through study day 10. Adverse events will be monitored through study day 10. Clinical outcomes, including all-cause mortality, ICU length of stay, and hospital length of stay will be assessed through hospital discharge.

## **STUDY ASSESSMENTS**

The assessment of efficacy will include collection of plasma for analysis of citrulline and arginine levels at 2 hours, 12 hours, and the alternating morning of study days the infusion is running for a maximum of

10 days, i.e., on days 2, 4, 6, 8 and 10. A patient will exit the study early if they have been weaned off all oxygen support before 10 days. Additional efficacy measures will include clinical outcomes, including progression of acute lung injury and lengths of hospital and ICU stay.

The assessment of safety will include collection of hemodynamic measurements at least every 4 hours on a hospital unit and--if a patient is critically ill in an ICU--hourly while the study material is infusing and for 12 hours after completion of the infusion in each patient. Hemodynamic measurements will be converted to a vasopressor dependency index for analysis if a patient becomes critically ill. Adverse event reporting will also serve as a means of safety analysis. Additional safety measures will be biochemical and hematologic laboratory measurements. The biochemical laboratory measurements, including liver function tests (ALT, AST, bilirubin, alkaline phosphatase), kidney function tests, D-dimer tests, CRP and electrolytes, along with hematologic laboratory measurements, including complete blood count and platelet count, will be collected when available for any study day in order to evaluate for adverse events.

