6.2 Inclusion Criteria

Participant eligibility is determined based on the selection of criteria detailed below:

1. Age 18-65 years.
2. Clinical evidence of COVID-19 (SARS-CoV2) infection, defined as a positive COVID-19 laboratory test plus evidence of an acute hypoxic respiratory illness requiring oxygen.
3. Admitted and transferred to floor without intubation.

6.3 Exclusion Criteria:

Patients meeting any of the following criteria will not be eligible for participation in the study:

1. No consent/inability to obtain consent
2. Patient, surrogate, or physician not committed to full support
3. Malignant or other irreversible condition and estimated 28-day mortality $\geq 50\%$
4. Moribund patient not expected to survive 48 hours (as defined by primary medical team) from start of study infusion
5. End-stage Liver Disease as defined by Child-Pugh Score > 9
6. Currently enrolled in, or participated in another study of an investigational compound within the last 30 days
7. Pregnant female, or female who is breast feeding
8. Allergy to L-citrulline or arginine or any citrulline- or arginine-containing product
9. Patient not otherwise suitable for the study in the opinion of any of the investigators
10. Requirement for intubation and invasive mechanical ventilation before study enrollment

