**Table 2: Secondary Safety Endpoints**

Safety Variables:	

1. Primary safety variable is hemodynamic status, specifically worst vasopressor dependency index through day 10.

2. Incidence of reported adverse events.

Safety Evaluations:	
In addition to vasopressor dependency index, the following laboratory values will be used for safety assessment at baseline and daily through study day 4 when available.
 

1. Complete blood count with platelets

2. Basic Metabolic profile, including renal function

3. Liver function tests, including SGOT, SGPT, total bilirubin, and alkaline phosphatase

 
Adverse events will be recorded prospectively, including incidences of hypotension, hepatitis (i.e., the elevation of liver enzymes), and injection site reactions.

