## **ANALYSIS POPULATIONS**

The intent-to-treat (ITT) population will be used for all efficacy and safety analyses. This will consist of all randomized patients irrespective of whether the patient received study drug or the patient's compliance with the study protocol, in the treatment group assigned by the randomization system.

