### **Missing Data**

Although every effort will be made to minimize the amount of missing data, some level of missing data will be unavoidable for a variety of reasons. In general, data may be missing due to subject's early withdrawal from study. Patients discontinuing early from the study and reasons for withdrawal will be summarized by treatment group to see if any biases in the analyses may have been created by any differences between groups. For the study of time-to-event endpoints, patients completing the study and not experiencing an event of interest are considered censored to the event. The impact of missingness will be minimized in the analysis of the primary endpoint by performing the analysis using Kaplan-Meier estimate, where participants will be censored at their last assessed time point. The procedures outlined below describing what will be done when data are missing may be refined during the blind review of the data.

For this Phase II study, missing data imputation will only be done for the primary and secondary biochemical outcomes (i.e., plasma levels of citrulline, arginine, ornithine, and NOx). For the analysis of other safety and secondary endpoints, no imputation will be done for missing values.

Missing biochemical data, it will be minimized operationally as we are setting up significant oversight on sample logistics. Nonetheless, given the longitudinal nature of data collection for biochemical measures, there exist the possibility of data truncation due to patient death.

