### **Statistical Method for the Safety Endpoint (Hemodynamic status)**

The vasopressor dependency index (VDI) is a continuous variable calculated by dividing vasopressor index (summation of all pressors) by the mean arterial blood pressure (MAP). VDI will be calculated at baseline (immediately before start of the infusion), 2 hours after completion of the bolus, and every 4 hours during the infusion. We will report descriptive statistics (mean  $\pm$  SD) of baseline and worst VDI separately for each treatment group. Worst VDI will be compared between groups using an analysis of covariance (ANCOVA) with the baseline VDI as the covariate.

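### The plan gives two rules for who has a vasopressor dependency index (VDI); read literally, one confines the main safety comparison to patients who become critically ill, and even with everyone scored the planned ANCOVA has low power to show more vasopressor use

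*SAP*

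**What the plan says.** **Role of the endpoint.** SAP Table 2 states: "Primary safety variable is hemodynamic status, specifically worst vasopressor dependency index through day 10". VDI is the vasopressor index divided by mean arterial pressure (SAP, Statistical Method for the Safety Endpoint; Protocol 7.1.3 and 10.5).

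**Rule 1, conditional.** SAP Study Assessments and Protocol 5.1.2 share one sentence: "Hemodynamic measurements will be converted to a vasopressor dependency index for analysis if a patient becomes critically ill". Critical illness is not defined for this purpose.

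**Rule 2, unconditional.** The SAP method section calculates VDI at baseline, then "2 hours after completion of the bolus, and every 4 hours during the infusion". Protocol 7.1.3 and 10.5 give the same schedule. Protocol 7.2.2 calculates it at its CRF recording times (2 h, 12 h and the daily morning reading), with vasopressor doses recorded where needed.

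**Analysis.** "Worst VDI will be compared between groups using an analysis of covariance (ANCOVA) with the baseline VDI as the covariate".

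**Who is analysed.** SAP Analysis Populations, like Protocol 10.1: "The intent-to-treat (ITT) population will be used for all efficacy and safety analyses". The next SAP section also defines an as-treated safety set; the point here is the same for either.

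**Missing values.** SAP Missing Data: "For the analysis of other safety and secondary endpoints, no imputation will be done for missing values".

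**Starting state.** Protocol 6.2 admits patients who are "Admitted and transferred to floor without intubation". Vasopressor use at entry is not expressly excluded.

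**The concern.** Protocol 11.5 names worsening hypotension as the theoretical risk of citrulline and VDI as the prespecified measure of it. An obvious form of that harm is more patients starting a vasopressor.

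Under Rule 1, a patient who never becomes critically ill has no VDI, is not imputed, and drops out of the ANCOVA. The arms are then compared in a subset formed after randomisation by an event the drug might cause, so the groups are no longer protected by randomisation. If more citrulline patients enter the subset, that excess is not itself part of the comparison.

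Under Rule 2, everyone has a value, but baseline VDI is likely to be 0 for nearly all floor patients, and worst VDI is a spike at 0 with a skewed tail. A comparison of means is then inefficient for detecting a larger number of users.

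Two programmers could therefore build different data sets for the main safety variable, and the choice might be made after the data are seen.

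**Working it through.** **Inputs.** From the documents: 60 analysable patients randomised 1:1, so 30 per arm (Sample Size sections); two-sided 0.05. The documents give no vasopressor rate, VDI spread, effect size or power for VDI, so there is no figure of the plan's own to reproduce. Assumptions: baseline VDI is 0 for all; worst VDI among users is lognormal with log-SD 0.7 to 1.0; unless stated, the distribution among users is the same in both arms. With a constant baseline, the ANCOVA reduces to a two-sample t test.

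**Expected differences.** Let p be the proportion on vasopressors (C placebo, T citrulline) and μ the mean worst VDI among users.
- Critically ill only, when critical illness coincides with vasopressor use: μ − μ = 0, whatever p_T and p_C are.
- Everyone, with 0 off vasopressors: (p_T − p_C)μ. For 30% versus 60% this is 0.30μ.
- Critically ill only, when 70% of each arm is critically ill regardless of drug and vasopressor use within that group is 30% versus 60%: 0.30μ in the subset. Overall rates are 0.7 × 30% = 21% and 0.7 × 60% = 42%, so the difference in everyone is 0.21μ.
- If critical illness coincides with use, and half of the citrulline users need half the dose: (0.5 × 1 + 0.5 × 0.5)μ − μ = −0.25μ in the subset, so the drug looks better even if it has added users.

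**Simulated chance of a significant result** (6,000 trials per scenario; ranges run over log-SD 0.7 to 1.0; simulation error about 1 percentage point):

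| Scenario, placebo v citrulline | Critically ill only, t test | Everyone, t test (= ANCOVA) | Everyone, rank test |
|---|---|---|---|
| Critical illness = vasopressor use, 30% v 60% | 4–5% | 28–40% | 60% |
| Same, 20% v 40% | 4% | 19–26% | 38% |
| Same, 10% v 20% | 3–4% | 9–13% | 18–19% |
| 70% critically ill in both arms, 30% v 60% on vasopressors within them | 22–31% | 20–28% | 40% |
| 50% users in both arms, dose doubled on citrulline | 30–63% | 20–36% | 10–15% |
| No difference, 30% v 30% | 4% | 3–5% | 5% |

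At 10% versus 20% the subset test cannot be run in about a fifth of trials because an arm has fewer than two users; these count as not significant. The rank test simulated is the unstratified Mann-Whitney, because the documents give no age split.

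**Direct comparison of proportions** (two-sided z, pooled variance under the null). At 30% v 60%: [0.30 − 1.96√(2 × 0.45 × 0.55/30)] / √((0.3 × 0.7 + 0.6 × 0.4)/30) = (0.300 − 0.252)/0.122 = 0.39, so power is 65%. At 10% v 20% the same formula gives 19%.

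**The case against.** A reader might infer that the plan excludes everyone who is not critically ill, so that its main safety test cannot see a doubling of vasopressor use. The documents do not support that.

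- The conditional sentence does not say that VDI is derived for no one else, and it sits in a general assessment paragraph. The methods text, the schedules and the ITT statement all point to a VDI for every patient.
- A patient on no vasopressor has 0/MAP = 0 by the definition. That is a computed value, so the no-imputation rule does not remove it.
- The 4–5% needs critical illness to coincide with vasopressor use, and users to be dosed alike in both arms. Protocol 5.1.2 links critical illness to ICU care, not to vasopressors. If critical illness is equal across arms, the subset test performs about as well as the test on everyone.
- Rule 1 would also leave the ANCOVA short of baselines, although these could be derived retrospectively for patients who later become ill.
- VDI is not the only route to a signal. Hypotension is collected as an adverse event and adverse events are tabulated by arm; VDI and hypotension are reviewed after 20 patients; individual VDI rises prompt review.

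Most of this stands, and the unconditional reading is at least as natural. What it does not remove is the contradiction: neither document states the zero rule, and the conditional sentence appears in both. The other routes are informal. No between-arm test of adverse events is specified, the 20-patient review uses the same undefined VDI alongside hypotension, and a percentage rise from baseline has no value when baseline is 0. Neither document compares the proportion of patients on vasopressors.

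A rank test is also not simply better. It loses power when only the dose rises, and at 10% versus 20% no method here does well.

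**Conclusion.** The point holds as an inconsistency in how the main safety variable is derived, together with low power for one plausible form of harm. It should be fixed, but it is not a fatal flaw.

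Under the literal conditional rule, the loss ranges from nearly complete (about 4–5% detection at 30% versus 60%, if critical illness coincides with vasopressor use) to negligible (22–31%, against 20–28% on everyone, if 70% are critically ill regardless of drug). Under the unconditional rule the analysis is not blind to the harm, only weak. A non-significant worst-VDI result would be little evidence of hemodynamic safety under either rule.

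The low-power conclusion rests on baseline VDI being near 0, which is likely but not guaranteed by the entry criteria, and on assumed rates and spread. The contradiction between the sections rests on the text alone.

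**What to change.** 1. **Protocol 5.1.2 and SAP Study Assessments:** delete the critical-illness condition.
2. **Protocol 10.5 and the SAP method section for hemodynamic status:** state that VDI is derived for every analysed patient at every scheduled time, baseline included, and equals 0 when no vasopressor is running. A time point with vasopressor use or the needed MAP unknown stays missing under the existing rule.
3. **Same SAP section:** report by arm the proportion of patients ever on a vasopressor through day 10, with a 95% CI for the difference.
4. **Keep the worst-VDI ANCOVA** and add an age-stratified Wilcoxon (van Elteren) test as a sensitivity analysis.

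Cost: wording and programming. Appendix A already schedules MAP and vasopressor doses for all patients on Days 1 to 11, so no new data are needed. The added test is a trade-off, which is why it supplements the ANCOVA: it gains when more patients need vasopressors (60% against 28–40% at 30% versus 60%) and loses when only the dose rises (10–15% against 20–36% for a doubling with 50% users). The wording should be settled before database lock.
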